### 3.2 Randomization and Blinding

Patients will be assigned treatment according to a 1:1:1 randomization schedule produced by inVentiv Health Clinical. The randomization code will not be available to the bioanalytical division of inVentiv Health Clinical until the clinical and analytical phases of the study have been completed.

Blinding of study treatments to the patient, site staff, and Sponsor will be maintained during the study using a double-dummy technique. Each patient will be dispensed with an IWRS-assigned kit, labeled with a unique kit ID at Visit 3, 4 and 5. Each kit will contain 3 bottles labeled with A, B, and C with 35 capsules each, which will be necessary to cover the period between 2 visits. The kits should be returned by the patient at the next visit and a new kit will be dispensed. Each patient should take 1 capsule from each bottle twice a day. The study will be double-blind. Patients will receive 1 of 3 different treatment kits, identical in appearance, as outlined in table below.

Treatment Group	Bottle A	Bottle B	Bottle C
IBD98-M 0.8 g/day	200 mg IBD98-M	200 mg IBD98-M	Matching Placebo
IBD98-M 1.2 g/day	200 mg IBD98-M	200 mg IBD98-M	200 mg IBD98-M
Placebo	Matching Placebo	Matching Placebo	Matching Placebo

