### 3.3 Sample Size Justification

Simon's randomized Phase 2 design was used. The average remission rate of placebo is approximately 0.2. With power of 0.8, and the difference in remission rates between the best treatment and the other treatments  $\geq 0.18$ , each arm requires 17 patients, giving the total number of patients to be enrolled as 51. This enrollment is adequate as it will provide 28.2% precision with a 95% confidence interval for evaluation of the difference between study treatment and placebo (i.e., the primary objective), where precision is defined as 1/2 width of the confidence interval. Based on this rationale, 51 patients will be enrolled, with 17 patients randomized to each group.

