### 7.8.1 Primary Efficacy Endpoint

The primary efficacy endpoint is the percentage of patients in remission at Week 6. A patient is considered to be in remission (a responder) at Week 6 if the patient has a modified UCDAI score of  $\leq 1$ , with a score of 0 for rectal bleeding and stool frequency, no mucosal friability (a mucosal appearance score of  $\leq 1$ ), and sigmoidoscopy (mucosal appearance) score not exceeding 1. A patient is considered to be a non-responder if no diary data is available within the period from Day 36 to study end or endoscopy within the period from Day 28 to study end (a non-responder imputation approach).

The number and percentage of patients who are in remission at Week 6 will be presented by treatment group, along with 95% confidence intervals constructed using the Clopper-Pearson method.

The percentage of patients in remission at Week 6 will be compared between each of the IBD98-M groups and placebo using Fisher's exact test. Each test will be 2-sided and declared statistically significant at the 0.05 level. No adjustment will be made for the two comparisons.

A bar chart of the percentage of patients in remission at Week 6 for each of the two IBD98-M groups and placebo will be presented.

As a supportive analysis, the primary efficacy endpoint will also be analyzed using the per protocol population.

Also, a sensitivity analysis will be used to assess the effects of missing data. The primary efficacy endpoint will be analyzed on the ITT population without making use of the non-responder imputation approach. Similar statistical methods will be used for the sensitivity analysis as is to be used for the primary efficacy analysis on the ITT population (which will use a non-responder imputation).

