#### Proportion of Patients With Clinical Improvement at Week 6:

The modified UCDAI score system includes four variables, namely rectal bleeding, stool frequency, mucosal appearance, and the physician's global assessment of disease activity. Each variable is scored from 0 – 3 so that the total score (a summation of the 4 variable scores) ranges from 0 – 12, with higher scores indicating more severe disease.

A patient will have experienced clinical improvement at Week 6 if the change from baseline (the last assessment prior to the first dose of study drug) to Week 6 (Visit 6) in the modified UCDAI score is  $\leq -3$ , where change is computed as the Week 6 modified UCDAI score minus the baseline modified UCDAI score. Only patients with a modified UCDAI score at baseline and Week 6 will have their clinical improvement status determined (no non-responder imputation).

The proportion of patients with clinical improvement at Week 6 will be summarized and analyzed using methodology similar to the primary efficacy endpoint for both the ITT and PP populations. A bar chart of the percentage of patients with clinical improvement at Week 6 by treatment group will be presented.

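### At 17 per arm Fisher's exact test leaves part of the 0.05 per-comparison error unused; Boschloo's exact test would recover some power within the same per-test limit, at a family-wise cost that should be stated

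*SAP*

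**What the plan says.** SAP 7.8.1 sets the primary test: the Week 6 remission percentage "will be compared between each of the IBD98-M groups and placebo using Fisher's exact test". On the error level it says "Each test will be 2-sided and declared statistically significant at the 0.05 level", and then "No adjustment will be made for the two comparisons". Protocol 12.4.1 names ANOVA, but Protocol 12 lets the SAP prevail where the two differ, so the Fisher sentence governs.

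SAP 3.3 gives the size. It states "Simon's randomized Phase 2 design was used" and "The average remission rate of placebo is approximately 0.2", and it arrives at 17 per arm (51 in total) from a power of 0.8 and a difference of at least 0.18 between the best arm and the others. SAP 3.2 allocates 1:1:1. Patients without Week 6 data count as non-responders for the primary endpoint, so every dosed patient stays in the denominator.

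For clinical improvement, SAP 7.8.2 says that the proportion "will be summarized and analyzed using methodology similar to the primary efficacy endpoint", and it treats endoscopic improvement in the same way. Neither of these endpoints is imputed.

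**The concern.** Fisher's test conditions on the total number of remissions. In small equal arms its attainable p-values are few and widely spaced, so the true chance of a false positive can lie well below the nominal level. The SAP allows 5% per comparison. If the test can use only about half of that, some results that could be declared significant within the same limit will not be. In a trial this small, that matters for the primary comparison, and the remedy would need no extra patients.

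**Working it through.** **Inputs.** 17 per arm, placebo rate 0.20 and difference 0.18 (so 0.38 on active) from SAP 3.3; two-sided 0.05 per comparison without adjustment from SAP 7.8.1. The active rates 0.45 and 0.50 are added here to show a range.

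**The plan's own figure.** Take three arms with true rates 0.20, 0.20 and 0.38 and break ties at random. The exact binomial probability that the best arm ranks first is 0.7896 at 16 per arm and 0.8004 at 17. So 17 is the smallest size that reaches 0.80, and the SAP's figure reproduces as a selection probability. It is not the power of the Fisher comparison.

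**Method.** List all 18 × 18 = 324 outcomes (a remissions on active, b on placebo). For a rejection region R:

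- Type I error at common rate p = Σ over R of Bin(a; 17, p) × Bin(b; 17, p).
- Power = Σ over R of Bin(a; 17, p₁) × Bin(b; 17, 0.20).
- Fisher's region: two-sided p ≤ 0.05.
- Boschloo's region: take Fisher's two-sided p-value as the statistic, find the probability of a value at least as small, maximise it over p, and reject if the maximum is ≤ 0.05.

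**Results at 17 v 17.**

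| | Fisher | Boschloo |
|---|---|---|
| Tables in the rejection region | 144 | 156 (all 144 included) |
| Maximum type I error | 0.0244 | 0.0431 |
| Type I error at 0.20 | 0.0194 | 0.0237 |
| Power, 0.38 v 0.20 | 11.7% | 17.4% |
| Power, 0.45 v 0.20 | 22.0% | 31.4% |
| Power, 0.50 v 0.20 | 31.9% | 43.1% |

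**Where the gain comes from.** Almost all of it lies in three added tables (active v placebo): 8 v 2, 9 v 3 and 10 v 4. With 3/17 on placebo, Fisher needs 10/17 on active (p = 0.032; 9/17 gives 0.071), while Boschloo accepts 9/17 (p = 0.035). At 0.38 v 0.20 the added probability is

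0.1431 × 0.1914 + 0.0877 × 0.2393 + 0.0430 × 0.2093 = 0.0274 + 0.0210 + 0.0090 = 0.0574.

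The other nine added tables bring 0.0003, so the gain is 0.0577, or 5.8 points. The same sum gives 9.4 points at 0.45 and 11.1 at 0.50.

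**Other placebo rates** (17 v 17, active 0.38 to 0.50): the gain is 5.6 to 9.0 points at placebo 0.10, 4.4 to 9.0 at 0.25 and 3.1 to 6.5 at 0.30.

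**Unequal arms** (placebo 0.20, active 0.38 to 0.50):

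| Active v placebo | Maximum size, Fisher | Maximum size, Boschloo | Gain in points |
|---|---|---|---|
| 17 v 16 | 0.035 | 0.040 | 3.1 to 4.0 |
| 16 v 17 | 0.035 | 0.040 | 3.3 to 3.8 |
| 17 v 15 | 0.034 | 0.047 | 3.3 to 4.4 |
| 15 v 17 | 0.034 | 0.047 | 3.4 to 7.9 |
| 16 v 15 | 0.030 | 0.048 | 4.5 to 8.9 |
| 15 v 16 | 0.030 | 0.048 | 5.9 to 9.0 |

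So unequal arms of 15 to 17 give about 3 to 9 points, with a maximum size of 0.048. If an arm reaches 18, the gain ranges more widely (2.6 points at 17 v 18 to 11.3 at 16 v 18, both for active 0.50), and the maximum size reaches 0.0499 at 16 v 18, still below 0.05.

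**Family-wise error**, both doses against one placebo arm of 17, all three rates equal to p. With q(b) the chance of rejection given b remissions on placebo, it is Σ over b of Bin(b; 17, p) × [1 − (1 − q(b))²].

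| Common rate | Fisher | Boschloo |
|---|---|---|
| 0.20 | 3.6% | 4.4% |
| 0.25 | 3.7% | 5.6% |
| Worst case | 4.5% (at 0.50) | 7.9% (near 0.38) |

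Boschloo exceeds 5% for common rates from about 0.23 to 0.77.

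**The case against.** The strongest reply is that the gain is paid for. Unadjusted Fisher tests at 17 per arm happen to hold the two-dose error at or below 4.5% at every common rate, and Boschloo gives that up. Adding only the first four of the 12 tables already lifts the worst case to 5.06%. The decision not to adjust was taken alongside Fisher's test, and the placebo rate of 0.20 is only approximate. This stands as a cost to disclose. It is not a breach of the plan, because SAP 7.8.1 limits error per comparison and sets no family-wise limit.

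Second, a reader might infer from the 17 v 17 figures that Fisher always wastes at least half of the allowed error, or that 6 to 11 points are assured. The documents do not support that. The ITT set leaves out patients who were never dosed, and SAP 3 sets 51 as an upper limit on enrolment, so the arms can end unequal. One patient fewer in either arm raises Fisher's maximum size to 3.5% and cuts the gain to 3 to 4 points. Boschloo itself uses only 2.4% at a common rate of 0.20. What does not depend on the arm sizes is that Boschloo's region contains Fisher's and its size cannot exceed 0.05.

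Third, the trial is exploratory, its size comes from a selection design, and Fisher's test is valid, prespecified and standard. All of that is true, and it limits how strongly the point can be put. It does not remove the point, since the SAP still declares significance at 0.05 on the primary objective.

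Fourth, no gain has been shown for clinical or endoscopic improvement. Those endpoints use observed cases, so their arm sizes are unknown, and no placebo rate is stated for them.

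**Conclusion.** The point holds as a recommended improvement. At exactly 17 v 17 and placebo 0.20, Boschloo's test adds 5.8, 9.4 and 11.1 points of power at active rates of 0.38, 0.45 and 0.50, with a maximum per-comparison error of 4.3% and no Fisher rejection lost. With unequal arms of 15 to 17 the gain is about 3 to 9 points.

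Two stronger readings should be resisted. The SAP is not in error: Fisher's test keeps its stated level. Nor does the change rescue the trial's power: 17.4% at the planned difference is still low, and the 0.8 in SAP 3.3 was never the power of this test.

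The figures assume independent binomial outcomes, all dosed patients in the denominator, and a test fixed before unblinding.

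**What to change.** Before unblinding, amend SAP 7.8.1 as follows:

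- Make Boschloo's two-sided exact unconditional test, at 0.05 for each dose against placebo, the primary test.
- Define it: Fisher's two-sided p-value as the statistic, maximised over the common rate, computed at the actual arm sizes.
- Require a validated program. At 17 v 17 the next four tables in the ordering would take the size to 0.0576, so a small slip at the boundary breaks the guarantee.
- Report Fisher's p-value as supportive.
- Name the interval for the difference in remission rates. SAP 6 asks for 95% intervals on treatment differences, and SAP 7.8.1 specifies only Clopper-Pearson intervals by group.
- State in the report that the two comparisons are unadjusted and that worst-case family-wise error is 7.9% (4.4% at a common rate of 0.20, 5.6% at 0.25).

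Using the same test for the binary secondary endpoints is optional, for consistency only. The cost is SAP wording, a short program with its validation, and the higher family-wise error; no patients are added.

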### 7.8.2 Secondary Efficacy Endpoint and Analyses

The secondary efficacy endpoints include:

Proportion of patients with clinical improvement at Week 6 (defined as a  $\geq 3$  point reduction from baseline in the modified UCDAI score)

Proportion of patients with endoscopic improvement at Week 6 (defined as a  $\geq 1$  point decrease from baseline in modified UCDAI mucosal appearance subscore)

Change in symptoms (rectal bleeding and stool frequency) from baseline to each study visit

#### Proportion of Patients With Clinical Improvement at Week 6:

The modified UCDAI score system includes four variables, namely rectal bleeding, stool frequency, mucosal appearance, and the physician's global assessment of disease activity. Each variable is scored from 0 – 3 so that the total score (a summation of the 4 variable scores) ranges from 0 – 12, with higher scores indicating more severe disease.

A patient will have experienced clinical improvement at Week 6 if the change from baseline (the last assessment prior to the first dose of study drug) to Week 6 (Visit 6) in the modified UCDAI score is  $\leq -3$ , where change is computed as the Week 6 modified UCDAI score minus the baseline modified UCDAI score. Only patients with a modified UCDAI score at baseline and Week 6 will have their clinical improvement status determined (no non-responder imputation).

The proportion of patients with clinical improvement at Week 6 will be summarized and analyzed using methodology similar to the primary efficacy endpoint for both the ITT and PP populations. A bar chart of the percentage of patients with clinical improvement at Week 6 by treatment group will be presented.

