##### Intention-to-Treat Population

The intent-to-treat (ITT) population will include all randomized patients who received at least one dose of study medication irrespective of any deviation from the protocol or premature discontinuation. The treatment group assignment will be designated according to initial randomization. The ITT population will serve as the basis for the analysis of efficacy.

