## 6. STATISTICAL CONSIDERATIONS

For efficacy and safety data, descriptive statistics (n, mean, standard deviation [SD], median, minimum, and maximum for continuous data, and n [%] for categorical data) will be presented. Similarly, wherever applicable, changes from baseline will be summarized in the same manner.

Unless otherwise stated, the denominator for percentages will be based on the number of patients in each treatment group who provided non-missing responses to the categorical variable, all statistical tests will be two-sided and at the 5% level of significance, and all differences between treatment groups will be presented with two-sided 95% confidence intervals (CIs). All p-values will be displayed to three decimals and rounded using standard scientific notation (e.g., 0.XXX). If a p-value less than 0.001 occurs it will be shown in tables as <0.001. If a p value greater than 0.999 occurs it will be shown in the tables as >0.999.

Unless otherwise stated, percentages will be presented to one decimal place in all summaries.

Minimum and maximum values will be presented to the same number of decimal places as collected on the case report form (CRF) or within the laboratory panel; mean and median will be presented to one decimal place more than CRF data; standard deviation will be presented to two decimal places more than CRF data.

Dates will be presented in format DDMMYY and numbering for tables, figures, and listings will follow ICH E3.

All statistical analyses will be performed using Statistical Analysis System (SAS®) version 9.4 or higher (SAS Institute, Cary, NC).

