#### Proportion of Patients With Endoscopic Improvement at Week 6:

A patient will have experienced endoscopic improvement at Week 6 if the change from baseline (the last assessment prior to the first dose of study drug) to Week 6 (Visit 6) in the modified UCDAI mucosal appearance score is  $\leq -1$ , where change is computed as the Week 6 score minus the baseline score.

Missing data will not be imputed at Week 6 if a patient has not made it to Week 6 and/or has no Week 6 mucosal appearance result.

The proportion of patients with endoscopic improvement at Week 6 will be summarized and analyzed using methodology similar to the primary efficacy endpoint for both the ITT and PP populations. A bar chart of percentage of patients with endoscopic improvement at Week 6 by treatment group will be presented.

Change in Symptoms (Rectal Bleeding and Stool Frequency) From Baseline to Each Study Visit:

Rectal bleeding is scored at each visit as normal (none), mild (streaks of blood), moderate (obvious blood), or severe (mostly blood). Stool frequency is scored at each visit as normal (none), mild (1-2 stools more than usual per day), moderate (3-4 stools more than usual per day), or severe ( $>4$  stools more than usual per day).

The number and percentage of patients with each categorical result will be presented for each symptom (rectal bleeding and stool frequency) at baseline (the last assessment prior to the first dose of study drug) and each post baseline visit for ITT and PP populations. Each IBD98-M group will be compared to placebo at each visit using Fisher's exact test.

A shift table will be prepared for each symptom, showing the number and percentage of patients with normal, mild, moderate, and severe results at baseline versus normal, mild, moderate, and severe results at each post-baseline visit, by treatment group.

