### **7.8.3 Exploratory Endpoint**

The exploratory endpoint is the reduction in fecal calprotectin.

Fecal calprotectin will be collected at Visit 3 (Week 0) and Visit 6 (Week 6) or early termination. Change from Visit 3 to Visit 6 or early termination will be computed as the Visit 6 value minus the Visit 3 value. Descriptive statistics (n, mean, standard deviation (SD), median, minimum,

and maximum) will be presented for observed fecal calprotectin at each visit and for change from Visit 3 at Visit 6 by treatment group for the ITT and PP populations.

Change from Visit 3 to Visit 6 in the fecal calprotectin will be analyzed as the response variable in an analysis of covariance (ANCOVA) model to compare each of the IBD98-M groups versus placebo. The model will include treatment as a fixed effect and the Visit 3 fecal calprotectin value as a covariate. The treatment-by-baseline interaction will be included in the model and if the term is not significant at the 0.10  $\alpha$ -level, it will be excluded from the model. If the interaction is significant at the 0.10  $\alpha$ -level, the interaction will be investigated and appropriate interpretation made or appropriate alternative methodology identified and implemented. Least squares means and associated 95% confidence intervals will be estimated for each treatment group, and the least squares mean difference (each IBD98-M group minus placebo) and associated 95% confidence interval will be estimated for each IBD98-M treatment group. Least square means will be compared between each active treatment group and placebo using two-sided testing at the  $\alpha = 0.05$  level. There will be no multiplicity adjustment.

The residuals from the above analyses will be checked for normality and homogeneity of variance. Normality will be examined by normal probability plots, while homogeneity of variance will be assessed by plotting the residuals against the predicted values for the model. Any deviation from either assumption may result in further analysis using an appropriate alternative transformation (such as logarithmic or power transformation) of the data or an alternative appropriate statistical analysis.

The analysis of the above exploratory efficacy endpoint will be repeated for the PP population.

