## **10. HANDLING OF MISSING VALUES AND OUTLIERS**

A non-responder imputation approach will be used for the primary efficacy endpoint data (see details in Section 7.8.1 of this SAP). No imputation will be done for secondary and exploratory endpoints. Missing data handling approaches for AE are in Section 7.9.1.

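### Clinical and endoscopic improvement are called ITT but scored only in patients with Week 6 data, with no missing-data sensitivity analysis and no rule for early-termination scores

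*SAP*

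**What the plan says.** SAP 4 defines the ITT population as randomised patients who took at least one dose, "irrespective of any deviation from the protocol or premature discontinuation". SAP 7.8 and 7.8.2 analyse both improvement endpoints on ITT and per-protocol populations, using methods like those for the primary endpoint.

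The scoring rules are narrower than that population:

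- **Clinical improvement (SAP 7.8.2):** "Only patients with a modified UCDAI score at baseline and Week 6 will have their clinical improvement status determined (no non-responder imputation"). Change is measured from baseline "to Week 6 (Visit 6) in the modified UCDAI score".
- **Endoscopic improvement (SAP 7.8.2):** "Missing data will not be imputed at Week 6 if a patient has not made it to Week 6", or if the Week 6 mucosal score is absent.
- **General rule (SAP 10):** "No imputation will be done for secondary and exploratory endpoints".
- **Denominators (SAP 6):** unless stated otherwise, "the denominator for percentages will be based on the number of patients in each treatment group who provided non-missing responses to the categorical variable".

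The one missing-data sensitivity analysis is in SAP 7.8.1: "The primary efficacy endpoint will be analyzed on the ITT population without making use of the non-responder imputation approach".

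The schedules in both documents give Visit 6 and early termination a single column. Protocol 10.1 schedules sigmoidoscopy at early termination, and Protocol 7.3 seeks every UCDAI subscale from patients who leave. For calprotectin, SAP 7.8.3 names early termination: "Change from Visit 3 to Visit 6 or early termination will be computed as the Visit 6 value minus the Visit 3 value". SAP 7.8.2 does not mention it.

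**The concern.** A table headed ITT would omit patients because of something that happened after randomisation. Under the supplied protocol (Synopsis and 7.3), rescue is not allowed during treatment and patients judged to be failing are withdrawn, so those omitted are probably non-improvers. Removing them raises the improvement rate in each arm. How far this distorts the comparison depends on how withdrawal falls between the arms.

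Whether this is a completers comparison turns on early-termination scores, and SAP 7.8.2 leaves that open. One programmer could take whatever sits in the shared column as Week 6. Another could read Week 6 as Day 42 and treat the same score as missing.

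Nothing else in the plan fills the gap. The SAP 7.8.1 sensitivity analysis works by dropping non-responder imputation, so carrying it over would only repeat the main secondary analysis. The per-protocol analysis does not help either, because SAP 7.2 makes missing primary efficacy data a major deviation. Disposition by arm (SAP 7.1) would reveal an imbalance but not correct for it.

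**Working it through.** The plan gives no figure on this point to reproduce. From the documents come 17 patients per arm (SAP 3.3) and the two-sided Fisher exact test at 0.05, unadjusted (SAP 7.8.1, carried to the secondaries by 7.8.2). Improver and withdrawal counts are assumptions.

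**1. Worked counts.** Everyone withdrawn is taken as a non-improver. Keeping all patients gives x/17; the observed-case rule gives x/(17 − m), where m is the number withdrawn with no counted score.

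| Improvers, active v placebo | Dropped | All patients kept | Observed cases |
|---|---|---|---|
| 11 v 5 | 4 v 4 | 64.7% v 29.4%: 35.3 points, p=0.084 | 11/13 v 5/13 = 84.6% v 38.5%: 46.2, p=0.041 |
| 11 v 5, early-termination score counted for 2 of 4 per arm | 2 v 2 | 35.3, p=0.084 | 11/15 v 5/15 = 73.3% v 33.3%: 40.0, p=0.066 |
| 9 v 6 | 2 v 5 | 17.6, p=0.49 | 9/15 v 6/12 = 60.0% v 50.0%: 10.0, p=0.71 |
| 8 v 8 | 4 v 4 | 0 | 8/13 v 8/13: 0 |
| 8 v 8 | 5 v 2 | 0 | 8/12 v 8/15: 13.3, p=0.70 |
| 10 v 4 | 1 v 0 | 10/17 v 4/17: p=0.080 | 10/16 v 4/17: p=0.037 |
| 12 v 5 | 0 v 2 | 12/17 v 5/17: p=0.038 | 12/17 v 5/15: p=0.074 |

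If all four early-termination scores per arm count in the first row, the difference stays at 35.3.

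**2. How often equal losses change the test result.** Over 5–13 active and 2–7 placebo improvers (9 × 6 = 54 combinations), k non-improvers were removed from each arm. The p-value crossed 0.05 in none for k=1 or k=2, in 3 for k=3, and in 6 for k=4. Outside this grid, very high counts can cross sooner: 15 v 9 with one lost per arm moves p from 0.057 to 0.037.

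**3. Expected difference.** Let r be the true improvement rate, d the share withdrawn and q the share of those withdrawn who had improved. The expected observed-case rate is (r − qd)/(1 − d). Take r = 0.50 v 0.30, a true difference of 20 points.

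With q = 0 and no early-termination score counted:
- 20%/20% withdrawn: 0.50/0.80 − 0.30/0.80 = 0.625 − 0.375 = 25.0 points
- 15%/30%: 0.50/0.85 − 0.30/0.70 = 0.588 − 0.429 = 16.0
- 30%/15%: 0.50/0.70 − 0.30/0.85 = 0.714 − 0.353 = 36.1

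If half the early-termination scores count, d is halved and the results are 22.2, 18.8 and 26.4. If all count, each is 20.0. With equal d and q = 0, the difference is the true difference divided by (1 − d), so it is zero when the true difference is zero.

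**4. If some withdrawn patients had improved.** With q = 0.25, the observed-case differences are:
- 20%/20%: 0.45/0.80 − 0.25/0.80 = 25.0
- 15%/30%: 0.4625/0.85 − 0.225/0.70 = 22.3
- 30%/15%: 0.425/0.70 − 0.2625/0.85 = 29.8

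Non-responder imputation gives (r₁ − qd₁) − (r₂ − qd₂):
- 20%/20%: 0.45 − 0.25 = 20.0
- 15%/30%: 0.4625 − 0.225 = 23.75
- 30%/15%: 0.425 − 0.2625 = 16.25

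Neither method is unbiased here in general.

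**The case against.** The strongest reply is that this is a declared choice. The SAP states the observed-case rule openly and consistently, Protocol 12 lets the SAP prevail, and ITT can be read as naming a set of patients rather than an imputation rule. That disposes of any charge of concealment. It does not supply a sensitivity analysis or settle what happens to early-termination scores.

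Second, the documents plan to collect full scores at early termination. If these are obtained and counted, most of the bias goes. This is correct, but SAP 7.8.2 does not say that they count, and its endoscopic rule can be read as saying that they do not.

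Third, the withdrawal provisions come from a protocol that appears not to be the Amendment 3 version on which the SAP is based: the SAP cites a Section 7.4 on re-screening that the supplied protocol lacks. Protocol 12.4.1 handles the improvement endpoints along the lines of the primary, but that may mean only the same test. So a departure from the protocol cannot be asserted on this text; it has to be checked against Amendment 3.

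Fourth, the sizes rest on assumed withdrawals, and equal losses of one or two per arm never crossed 0.05 in the grid. That stands for equal losses. Unequal losses act sooner, as the 10 v 4 example shows.

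Last, non-responder imputation can also mislead. In the 15%/30% scenario with q = 0.25, the SAP's rule is closer to the truth (22.3 against 23.75, true value 20); in the other two it is further off. This is a reason to report both analyses.

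**Conclusion.** The concern holds and should be fixed. Followed as written, SAP 7.8.2 and 10 drop patients without Week 6 data from a result labelled ITT, provide no missing-data sensitivity analysis for either improvement endpoint, and leave early-termination scores unmapped.

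If those withdrawn are non-improvers and no early-termination score counts, a true 20-point difference is expected to appear as 16.0 to 36.1 points over the withdrawal patterns examined. Equal withdrawal enlarges a real difference but creates none under the null. Withdrawal heavier on active inflates the difference, and withdrawal sufficiently heavier on placebo shrinks it. These sizes depend on assumed withdrawal and improvement rates; the textual gaps do not. Only secondary results in an exploratory trial are affected.

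**What to change.** Before unblinding, amend SAP 7.8.2 and 10 as follows:

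- Keep every ITT patient in the denominator for both improvement endpoints, and count as non-improvers those lacking the data the endpoint needs.
- Reuse the SAP 7.8.1 windows. Endoscopic improvement needs endoscopy from Day 28 to study end; clinical improvement needs that endoscopy plus diary data from Day 36 to study end.
- State that early-termination scores within these windows count as Week 6. Take the Physician's Global Assessment from the same Visit 6 or early-termination visit, with no new window for it.
- Keep the observed-case analysis as a sensitivity analysis for both endpoints.
- Compare the result with Protocol Amendment 3 and record any difference in SAP 14.

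The cost is SAP wording, two derivations and one mapping rule. Improvement rates will be somewhat lower, and withdrawals unrelated to efficacy will count as failures, so the estimate can err in either direction. A patient leaving between Day 28 and Day 35 may be observed for endoscopic improvement yet count as a clinical non-improver. Endoscopies before Day 28 will not count, and scores taken after alternative treatment starts remain unaddressed; both limits are inherited from SAP 7.8.1. Reporting both analyses shows how much the choice matters.
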